### 3.2. Phase 1 Design

The primary objective of Phase 1 is to determine the Maximum Tolerated Dose (MTD) and the Recommended Phase 2 Dose (RP2D) of DS-1594b when administered as a single agent in subjects with relapsed or refractory AML or ALL, including subjects with or without MLLr or NPM1m using a Bayesian optimal interval (BOIN) design to find the MTD.

The BOIN design is implemented in a simple way similar to the traditional 3+3 design but is more flexible and possesses superior operating characteristics that are comparable to those of the more complex model-based designs, such as the continual reassessment method (CRM).

At least 3 subjects must be enrolled at each dose level. If a dose level is found to be safe by the BOIN design we will escalate to the next higher dose level. The SRC can recommend additional enrollment of up to 9 additional subjects per dose level for dose levels that have already been deemed to be safe with the intent to gain additional information on safety, efficacy and PK at different dose levels, and to guide selection of optimal biologically effective RP2D. These additional 9 subjects per dose level will not be considered evaluable for DLTs. It is anticipated that approximately 18 subjects will be added in this Phase 1 expansion.

Although all R/R ALL and R/R AML subjects, irrespective of mutations, will be allowed during the Phase 1 dose-escalation the goal is to treat at least 3 subjects with MLLr or NPM1m are included at dose levels that are anticipated to be biologically active to allow for optimal evaluation of safety and efficacy in the presumed target population to guide selection of the optimal RP2D.

Treatment during Phase 1 dose escalation phase will follow continuous oral administration under a twice-daily schedule or daily schedule on a 28-day dosing cycle.

The first dose cohort will start at 70 mg twice daily, approximately every 12 hours. The target toxicity rate for the MTD is  $\phi = 0.2$  and the maximum sample size for determining the MTD is 42. Each cohort will include a minimum of 3 subjects. The DLT evaluation period will be limited to the first 28 days of dosing. DLTs are defined in Section 3.2.2 and only those DLTs that occur within the first cycle (28 days) will be used for dose finding. As shown in [Figure 2](#), the BOIN design uses the following rule, optimized to minimize the probability of incorrect dose assignment, to guide dose escalation/de-escalation:

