  - b. When we eliminate a dose, automatically de-escalate the dose to the next lower level. When the lowest dose is eliminated, stop the trial for safety. In this case, no dose should be selected as the MTD.
  - c. If none of the actions (i.e., escalation, de-escalation or elimination) is triggered, treat the new subjects at the current dose.
  - d. If the current dose is the lowest dose and the rule indicates dose de-escalation, treat the new subjects at the lowest dose unless the number of DLTs reaches the elimination boundary, at which point terminate the trial for safety.
  - e. If the current dose is the highest dose and the rule indicates dose escalation, treat the new subjects at the highest dose.

Formatted: C-Hyperlink

Formatted: C-Hyperlink

3. Repeat step 3 until the maximum sample size of 30 is reached or stop the trial if the number of subjects treated at the current dose reaches 9 and the decision according to [Table 4](#) is to stay at the current dose.

Formatted: C-[Hyperlink](#)

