## **9. STATISTICAL CONSIDERATIONS**

This is an open-label Phase 1/2 multi-arm study. The primary objective in Phase 1 is to determine the Maximum Tolerable Dose (MTD) and identify the Recommended Phase 2 Dose (RP2D) of DS-1594b.

Phase 2 will evaluate the safety and response rate within 3 months of therapy initiation with single agent or combinations of DS-1594b at the RP2D in the following 4 cohorts:

- Cohort A: R/R AML with MLL-rearrangement,
- Cohort B: R/R AML with NPM1 mutation,
- Cohort C: R/R AML treated with the combination of azacitidine and venetoclax with DS-1594b

- Cohort D: R/R ALL treated with the combination of miniHCVD with DS-1594b.

Up to 182 subjects will be enrolled in the study (approximately 66 subjects in Phase 1 (i.e. up to 42 for dose titration-BOIN design, 6 for food effect sub-studies, and up to 18 for refining RP2D at safe doses below or at the MTD and DDI sub-studies) and up to 26 subjects per cohort in Cohorts A-and B and up to 32 subjects per cohort in Cohorts C and D in Phase 2).

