### **9.2. Phase 2**

The primary endpoint of cohorts A-C is the achievement of CR + CRh within 3 months of therapy initiation in subjects with R/R AML with MLLr or NPM1m. The primary endpoint of cohort D is the achievement of CR + CRI within 3 months of therapy initiation in subjects with R/R ALL with MLLr. Up to 26 subjects will be enrolled per cohort in Cohorts A and B and up to 32 subjects will be enrolled per cohort in Cohorts C and D. Each cohort will be analyzed separately. Treatment will be considered encouraging if the CR/CRh rate (Cohorts A, B, and C) or CR/CRI rate (Cohort D) rate would reach at least 40%, an improvement over the historical rate by more than 15%. The study will monitor futility and toxicity using the Bayesian method of Thall, Simon and Estey.

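### BOIN step 3 ends dose-finding at 30 subjects, while the main text of Section 3.2 and Section 9 set the maximum at 42, and Table 5 does not describe the written rule at either cap

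*Combined protocol and SAP*

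**What the plan says.** Section 3.2 sets the target DLT rate at 0.20 and states that "the maximum sample size for determining the MTD is 42". The numbered steps later in that section put the design into operation. Step 1 treats three subjects at dose level 1. Step 2 assigns the next cohort's dose from Table 4. Step 3 says when to stop: "Repeat step 3 until the maximum sample size of 30 is reached or stop the trial if the number of subjects treated at the current"; the rest of that sentence ties the early stop to nine subjects at one dose and a stay decision from Table 4. The MTD is then selected by isotonic regression.

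Section 9 budgets "up to 42 for dose titration-BOIN design, 6 for food effect sub-studies, and up to 18 for refining RP2D" and the DDI sub-studies, under the statement "Up to 182 subjects will be enrolled in the study (approximately 66 subjects in Phase 1". Section 9.2 adds: "Up to 26 subjects will be enrolled per cohort in Cohorts A and B and up to 32 subjects will be enrolled per cohort"; the second figure is for the combination cohorts.

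Sections 3.2 and 9.1 evaluate the QD and BID regimens separately under the BOIN rule. Neither says whether the maximum is per regimen or shared. Section 3.2.1 introduces Table 5 as 1000 simulations of the design and does not name the cap used.

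**The concern.** Two current passages give different values for the same stopping threshold. Suppose 30 subjects have been treated and Table 4 still calls for another cohort. One passage ends dose-finding and triggers MTD selection; the other allows up to 12 more subjects (42 − 30). As written, that choice could be made after the DLT data have been seen.

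Step 3 also tells the team to repeat step 3, which is itself, although dose assignment is in step 2. The step that governs the end of escalation therefore needs correcting in two places.

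**Working it through.** **1. Enrolment totals.** Inputs are from Sections 9 and 9.2.
- With 42: 42 + 6 + 18 = 66, and 66 + 2×26 + 2×32 = 182. Both stated totals are reproduced exactly.
- With 30: 30 + 6 + 18 = 54, and 54 + 52 + 64 = 170. Neither matches.

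**2. When the other stopping rule can apply.** At nine subjects Table 4 escalates at 0–1 DLTs, de-escalates at 3 and eliminates at 4 or more. Only exactly 2 DLTs means stay. Steps 2d and 2e also hold subjects at the lowest or highest dose when no move is possible. Step 3 does not say whether that counts as a stay, so both readings were simulated.

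**3. Boundaries.** With target 0.20 and the standard limits 0.6×0.20 = 0.12 and 1.4×0.20 = 0.28:
- escalate: ln(0.88/0.80) / ln[(0.20×0.88)/(0.12×0.80)] = 0.1572 (plan: 0.157)
- de-escalate: ln(0.80/0.72) / ln[(0.28×0.80)/(0.20×0.72)] = 0.2385 (plan: 0.238)

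Elimination uses Pr(p > 0.2) > 0.95 under Beta(1+y, 1+n−y). All three boundaries match Table 4 for n = 3 to 9.

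**4. Simulation of the written rules.** Cohorts of 3, one regimen, no SRC override, the true DLT rates of Table 5, isotonic MTD selection, 20,000 trials per scenario.

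| Scenario | 1 | 2 | 3 | 4 | 5 | 6 |
|---|---|---|---|---|---|---|
| *Stop at 9 if the dose cannot change* | | | | | | |
| Ended by cap 30, % | 4.3 | 12.1 | 19.4 | 27.0 | 36.7 | 38.7 |
| Ended by cap 42, % | 1.4 | 3.6 | 5.8 | 7.6 | 10.0 | 8.4 |
| Correct MTD, cap 30, % | 63.7 | 50.0 | 52.0 | 47.4 | 39.7 | 44.9 |
| Correct MTD, cap 42, % | 64.3 | 50.6 | 54.5 | 51.0 | 44.2 | 49.8 |
| Difference, points | 0.6 | 0.6 | 2.5 | 3.6 | 4.5 | 4.9 |
| *Literal: stop at 9 only if Table 4 says stay* | | | | | | |
| Ended by cap 30, % | 15.1 | 34.1 | 45.5 | 51.9 | 57.9 | 61.3 |
| Ended by cap 42, % | 9.2 | 22.8 | 29.7 | 31.6 | 33.7 | 35.5 |
| Correct MTD, cap 30, % | 61.4 | 50.4 | 52.3 | 48.3 | 39.8 | 45.1 |
| Correct MTD, cap 42, % | 62.1 | 51.6 | 54.8 | 51.4 | 44.6 | 49.0 |

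Smaller runs of the same rules (4,000 to 8,000 trials per scenario) agree on the cap shares to within about 2 points. They put the loss in correct selection as high as about 8 points, so 0–8 is the cautious range.

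**5. Table 5 against the written rule.** Average sample sizes:

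| Scenario | 1 | 2 | 3 | 4 | 5 | 6 |
|---|---|---|---|---|---|---|
| Table 5 | 18.2 | 22 | 23.7 | 23.6 | 22.9 | 19.7 |
| Written rule, cap 30 | 13.4 | 18.8 | 22.6 | 24.7 | 26.1 | 26.3 |
| Written rule, cap 42 | 13.8 | 19.7 | 24.1 | 26.8 | 29.0 | 29.1 |

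The two lower rows use the first reading of the stop-at-9 rule. Neither cap reproduces Table 5.

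The table also conflicts with the minimum cohort of 3. Its shares imply average numbers at dose 1 of 8.4% × 23.7 = 2.0 (Scenario 3), 6.2% × 23.6 = 1.5 (Scenario 4), 5.4% × 22.9 = 1.2 (Scenario 5) and 6.6% × 19.7 = 1.3 (Scenario 6). Every trial starts with three subjects at dose 1, so no average can be below 3.

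**The case against.** **The consequence can be overstated.** A reader might infer that a cap of 30 often ends escalation before the MTD is located. The documents do not support that. A trial that reaches the cap still selects an MTD by isotonic regression, unless the lowest dose has been eliminated. In the simulation the true MTD dose is untried when a cap of 30 ends the trial in 0–12% of trials (0–17% on the literal reading), with the high values in Scenarios 5 and 6. The RP2D is also an SRC decision and need not equal the MTD.

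**The larger cap shares depend on the reading.** The 15–61% range holds only if enrolment continues past nine at a dose the trial cannot leave, and on that reading a cap of 42 also binds in 9–36%. If the SRC also uses its Table 4 option to stay after one DLT in three, under the first reading, a cap of 30 ends 4–26% of trials. These points stand. They reduce the effect but do not remove the contradiction.

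**Parallel regimens.** It is tempting to say that QD and BID together would use up 30 sooner. That holds only for a shared cap, which the plan does not state, and it was not simulated. A reader might equally suppose 30 per regimen within 42 overall; no text says so.

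**How Table 5 was produced.** A variant with single-subject accelerated titration before cohorts of 3, capped at 30, comes within 0.4 of every average sample size in Table 5; capped at 42 it runs 1.0 to 1.9 too high. This suggests a cap of 30 behind Table 5, but the plan mentions no such titration, so it remains an inference.

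**A cross-reference slip.** The self-reference in step 3 is plainly a slip and would probably be read as intended. The Figure 2 flowchart is not visible in the available text and could not be checked for a cap.

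**Conclusion.** The contradiction stands: 30 in step 3 against 42 in the main text of Section 3.2 and in Section 9, with the totals of 66 and 182 met only by 42. Section 9's sums are correct; the fault is inconsistency over a threshold that decides when dose-finding ends.

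The effect is modest. It is smallest when the MTD is at a low dose level and largest when it is high: on the first reading, a cap of 30 ends 27–39% of trials in Scenarios 4–6, against 8–10% at 42. The selection loss is about 0–8 points, and 0.6–4.9 in the largest run. These figures assume one regimen, cohorts of exactly 3, no SRC override and the DLT rates of Table 5.

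Separately, Table 5 cannot support either cap as it stands, because its numbers at dose 1 are impossible under the written minimum of 3.

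**What to change.** - Reconcile the passages to one cap. If 42, change step 3. If 30, change the main text of Section 3.2 and Section 9, and restate the totals as 54 and 170.
- In step 3, replace the reference to step 3 with step 2.
- State whether the cap applies per regimen or is shared by QD and BID. Two regimens at 30 each could need 60, and at 42 each 84; both exceed the 42 budgeted in Section 9.
- Say whether nine subjects at a dose the trial cannot leave counts as a stay.
- Rerun Table 5 under the chosen cap and the written minimum of 3 per cohort, and name the cap and cohort size in Section 3.2.1.

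The text changes are short, and a cap of 42 adds no subjects to the stated totals. This is more than a one-line amendment, though: changing only the number in step 3 would leave the operating characteristics describing a different design. The rerun is a small simulation task.

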Formatted: C-Hyperlink

- if the observed DLT rate at the current dose is 0.157 or less, escalate the dose to the next higher dose level;
- if the observed DLT rate at the current dose is more than 0.238, de-escalate the dose to the next lower dose level;
- otherwise, stay at the current dose.

Evaluation by the abovementioned BOIN rule will be done for each dose level separately based on the cumulative number of DLT evaluable subjects treated in that dose level and regimen (i.e., QD or BID). In case the multiple dosing regimens are initiated simultaneously and parallel enrollment is allowed in the multiple dosing regimens, the evaluation by the BOIN rule for each dose level and regimen would be made separately. DLT observed after intra-patient dose escalation (IPDE) will not be considered in the dose escalation/de-escalation decision (See Section 6.9 for details about IPDE). For the purpose of overdose control, doses  $j$  and higher levels will be eliminated from further examination if  $\Pr(p_j > 0.2 | \text{data}) > 0.95$  and at least 3 subjects have been treated at dose level  $j$ , where  $p_j$  is the true DLT rate of dose level  $j$ ,  $j = 1, \dots, 6$ . This posterior probability is evaluated based on the beta-binomial model  $y_j | p_j \sim \text{binomial}(p_j)$  with  $p_j \sim \text{uniform}(0,1)$ , where  $y_j$  is the number of subjects who experienced DLT at dose level  $j$ . When the lowest dose is eliminated, stop the trial for safety. The probability cutoff 0.95 is chosen to be consistent with the common practice that when the target DLT rate  $\leq 1/6$ , a dose with 2/3 subjects experienced DLT is eliminated. The above dose escalation/de-escalation and elimination rule can be equivalently presented in [Table 4](#), which will be used to conduct the trial.

Formatted: C-Hyperlink

The steps to implement the BOIN design are described as follows:

1. Three subjects in the first cohort are treated at dose level 1 (70 mg twice daily). Each cohort will include a minimum of 3 subjects.
2. To assign a dose to the next cohort of subjects, conduct dose escalation/de-escalation according to the rule displayed in [Table 4](#). When using [Table 4](#), please note the following:
  - a. “Eliminate” means eliminate the current and higher doses from the trial to prevent treating any future subjects at these doses because they are overly toxic.

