**Table 4: Dose escalation/de-escalation rule for the Boin design**

[figure not shown]
Number of subjects treated at current dose	3	4	5	6	7	8	9
Escalate if number of DLTs is less than or equal to	0	0	0	0	1	1	1
De-escalate if number of DLTs equal to or greater than	1*	1*	2	2	2	2	3
Eliminate if number of DLTs equal to or greater than	2	3	3	3	4	4	4

Note. # of DLT is the number of subjects with at least 1 DLT in the first 28 days of dosing. Observations from IPDE will not be considered (Section 6.9). When none of the actions (i.e., escalate, de-escalate or eliminate) is triggered, stay at the current dose for treating the next cohort of subjects. \*The SRC can decide to enroll an additional 3 subjects at this dose level. In case the multiple dosing regimens are initiated simultaneously and parallel enrollment is allowed in the multiple dosing regimens, the evaluation for Boin rule for each dose level and regimen would be made separately.

In [Table 4](#), if 1 out of 3 or 4 subjects experience a DLT in the first cycle of treatment, the algorithm recommends dose de-escalation, rather than staying at the current dose. Considering only information from 3 to 4 subjects will be initially available, the incidence of 1 DLT does not sufficiently establish that the MTD is exceeded. Under this situation, a recently published i3+3 design recommends staying in the current dose level if the observed number of DLTs is only 1 greater than the number required for dose escalation. Therefore, the Safety Review Committee could decide to enroll an additional 3 subjects at that dose level, if only 1 of 3 or 4 subjects experiences a DLT.

Formatted: C-[Hyperlink](#)

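### Step 3 stops dose-finding early only on 2 of 9 DLTs, so a dose whose next move is blocked keeps enrolling; Table 5 does not appear to have been simulated under that stop

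*Combined protocol and SAP*

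**What the plan says.** Step 3 of the BOIN procedure in Section 3.2 repeats dose assignment up to a maximum sample size, with one earlier exit. It begins "stop the trial if the number of subjects treated at the current dose reaches 9 and the decision according to" and ends by requiring that Table 4 gives a stay. The note under Table 4 defines that decision: "When none of the actions (i.e., escalate, de-escalate or eliminate) is triggered, stay at the current dose". At 9 subjects the boundaries are escalate at 1 or fewer DLTs, de-escalate at 3 or more, eliminate at 4 or more.

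Two notes on using Table 4 cover moves that cannot be made. Step 2e: "If the current dose is the highest dose and the rule indicates dose escalation, treat the new subjects at the highest dose". Step 2d: "If the current dose is the lowest dose and the rule indicates dose de-escalation, treat the new subjects at the lowest dose unless", with elimination as the exception. Neither mentions the early exit. Step 2a says that elimination means to "eliminate the current and higher doses from the trial to prevent treating any future subjects at these doses", but no step says what to do when Table 4 then indicates escalation into a closed level.

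Of Table 4 the section says: "The above dose escalation/de-escalation and elimination rule can be equivalently presented in" it. The table ends at 9 subjects. The cap is 30 in step 3, but earlier in Section 3.2 "the maximum sample size for determining the MTD is 42", and Section 9 also allows up to 42 for this part.

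**The concern.** Once 9 subjects have been treated at the highest dose with 0 or 1 DLT, the procedure has nowhere higher to go. The step 3 exit still does not apply, because the Table 4 decision is to escalate. Enrolment continues at that dose, the next cohort of 3 brings it to 12, and Table 4 has no column for 12. Step 2d produces the same situation at the lowest dose with 3 of 9, where the observed DLT rate is above target. By inference from steps 2a and 2e it also arises at any dose whose next level has been eliminated.

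Two things are at stake. First-in-human subjects may be enrolled in dose-finding after the rule has no further move to make. And Table 5, which is offered as evidence that the design works, may describe a different stopping rule from the one the site would follow.

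**Working it through.** **Inputs.** From Section 3.2: target DLT rate 0.2; thresholds 0.157 and 0.238; elimination if Pr(p > 0.2 | data) > 0.95 with a uniform prior and at least 3 subjects; first cohort of 3; six dose levels; caps of 30 and 42. From Table 5: true DLT rates and mean sample sizes. Assumption: the usual BOIN alternatives 0.6 × 0.2 = 0.12 and 1.4 × 0.2 = 0.28.

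**Reproducing the plan's boundaries.**
- Escalation: ln(0.88/0.80) / ln[(0.20 × 0.88)/(0.12 × 0.80)] = 0.0953/0.6061 = 0.157.
- De-escalation: ln(0.80/0.72) / ln[(0.28 × 0.80)/(0.20 × 0.72)] = 0.1054/0.4418 = 0.238.
- Elimination at 9 subjects: 3 DLTs give Beta(4, 7) and Pr(p > 0.2) = 0.879; 4 DLTs give Beta(5, 6) and 0.967. The boundary is 4.

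Every column of Table 4 from 3 to 9 reproduces.

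**What stay means at 9.** 1/9 = 0.111 (escalate), 2/9 = 0.222 (stay), 3/9 = 0.333 (de-escalate, not eliminated). Only 2 of 9 ends the trial. At a true rate of 0.20:
- P(0 or 1 of 9) = 0.8^9 + 9 × 0.2 × 0.8^8 = 0.436.
- P(2 of 9) = 36 × 0.2^2 × 0.8^7 = 0.302.

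At a true rate of 0.10 these are 0.775 and 0.172. The better tolerated the dose, the less likely the exit.

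**Effect on sample size.** The written steps were simulated with cohorts of 3 and no SRC override, with at least 5,000 trials per scenario. Mean N is shown with the literal stop and with a stop added at 9 when escalation is indicated but no higher dose is open.

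| Table 5 scenario | 1 | 2 | 3 | 4 | 5 | 6 |
|---|---|---|---|---|---|---|
| Cap 30, literal | 16.5 | 22.2 | 25.6 | 26.8 | 27.6 | 27.9 |
| Cap 30, added stop | 14.5 | 18.9 | 22.7 | 24.7 | 26.2 | 26.4 |
| Cap 42, literal | 18.0 | 25.5 | 30.2 | 31.9 | 33.1 | 33.8 |
| Cap 42, added stop | 15.0 | 20.0 | 24.3 | 26.9 | 28.9 | 29.0 |

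The saving is about 1.5 to 3.3 subjects at cap 30 and about 3 to 6 at cap 42. With a flat 5% DLT rate at all six doses and cap 42, mean N falls from about 37 to about 27. Correct MTD selection changes by about 2 points at most. Also stopping on a blocked de-escalation at the lowest dose takes scenario 1 (cap 42) from 15.1 to 13.7 in a separate run.

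**Comparison with Table 5.** In scenario 6 Table 5 puts 6.6% of 19.7 subjects at dose 1: 0.066 × 19.7 = 1.3. That is below the stated minimum of 3, so a single-subject start is inferred. With that start and cap 30:

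| Scenario | 1 | 2 | 3 | 4 | 5 | 6 |
|---|---|---|---|---|---|---|
| Table 5 | 18.2 | 22 | 23.7 | 23.6 | 22.9 | 19.7 |
| Literal stop | 21.0 | 24.7 | 26.1 | 26.4 | 25.5 | 24.7 |
| Blocked moves also stop | 18.1 | 21.9 | 23.3 | 23.4 | 22.4 | 20.0 |

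The fit in scenarios 1 to 5 depends on how the single-subject start is coded. In a further run that tops up the dose of the first DLT to 3, the literal stop came within 1.5 subjects of Table 5 in those five scenarios. Scenario 6 is the one that discriminates: the literal stop gives about 24 to 34 across both caps and both kinds of start, against 19.7.

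**The case against.** **Step 2e can be read as a stay.** Steps 2a to 2e are notes on using Table 4, so treating at the highest dose again could count as staying, and the exit would then apply. Table 5 is consistent with that reading. This stands as a plausible account of what was intended. But step 3 refers to the Table 4 decision, and step 2e applies when the rule indicates escalation. Two readings that differ by several subjects on average need one wording. Figure 2 is not reproduced in the text available and may be clearer.

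**The top-dose case alone is small in most scenarios.** This stands. Under the literal rule at cap 42, dose 6 exceeds 9 subjects in at most 6.3% of trials in scenarios 1 to 5, and in 31% in scenario 6. Most of the avoidable enrolment in the other scenarios comes from doses below an eliminated level, where continuing is inferred and not written.

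**A reader might infer that the defect affects the 48 to 64% of trials in which some dose exceeds 9 subjects.** The design does not support that. Ordinary movement between doses also takes a dose past 9, and about 23 to 38% of trials still do so at cap 42 once blocked escalation stops the trial.

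**A reader might also infer that no rule exists past 9 subjects.** That is not so. The thresholds and the posterior elimination rule in Section 3.2 work at any count; only the printed table ends.

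**Oversight and extra data.** SRC review of each BOIN recommendation (Section 3.2.1), tentative dose levels (Figure 1 note) and the sponsor's right to terminate (Section 8.9.2) soften the effect, but none is a prespecified stop. Extra subjects at the top dose do have value, since Section 3.2 says the additional subjects at safe doses are not evaluable for DLTs.

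**Conclusion.** The gap is real on the written text and moderate in size. The early exit fires only on 2 of 9. It does not fire at the highest dose with 0 or 1 of 9, at the lowest dose with 3 of 9, or, by inference, at a dose below an eliminated level. Closing the blocked-escalation part saves about 1.5 to 3.3 subjects on average at cap 30 or about 3 to 6 at cap 42 in the Table 5 scenarios, and about 10 if all doses have a 5% DLT rate (cap 42), with little effect on MTD selection. These figures assume cohorts of 3 and no SRC override.

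Step 3 also does not appear to match the design behind Table 5. That rests mainly on scenario 6 and on a single-subject start that the plan does not state. It would go too far to call Table 5 wrong, or to say that the design as intended wastes subjects. The documents support only a mismatch between the written stop and the reported operating characteristics.

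**What to change.** 1. Reword step 3 so that dose-finding stops when the current dose has reached 9 subjects and the decision is either to stay or a move that cannot be made: escalation with no higher dose open (top level, or next level eliminated), or de-escalation at the lowest dose.
2. Give one cap; 30 and 42 must be reconciled.
3. Confirm that Table 5 was produced under the stated stop, cap and cohort size, or rerun it.
4. Extend Table 4 with the same rule, because movement between doses still takes some doses past 9.

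| Subjects | Escalate at or below | De-escalate at or above | Eliminate at or above |
|---|---|---|---|
| 10–12 | 1 | 3 | 5 |
| 13 | 2 | 4 | 5 |
| 14–15 | 2 | 4 | 6 |

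Continue the table to the cap.

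The editing cost is one sentence, some table columns and possibly one simulation run. There are two design costs. Fewer DLT-evaluable subjects accrue at the top dose, and the expansion does not replace them. Stopping at the lowest dose also gives fewer chances to reach the elimination boundary. In one run of scenario 1 (cap 30, single-subject start, 1 of 3 DLTs handled by adding subjects), stops for toxicity fell from 15.0% to 11.1% when blocked moves in both directions ended the trial. Step 3 should therefore also state how the MTD is declared after a stop at the lowest dose.
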